4.0 Drug Information

Oxandrolone is an orally administered synthetic derivative of the hormone testosterone, and is classified as an anabolic steroid. In males, testosterone has many vital functions such as the development and support of reproductive organs, increased skeletal muscle mass, bone mineral density, and growth of facial and body hair.

Oxandrolone is approved by the Federal Drug Administration (FDA) in patients who have lost weight resulting from extensive surgery, severe trauma, chronic infection, or as an adjunctive therapy to promote weight gain. It is also approved for bone pain associated with osteoporosis, and to attenuate protein catabolism associated with the prolonged use of corticosteroids. Oral administration of Oxandrolone has demonstrated increases in lean mass, protein synthesis, and wound healing with no long-term adverse events in trauma patients as well as healthy male controls.¹⁻³ Elevated liver transaminase levels have been noted but have been transient and asymptomatic.¹⁻³ The aforementioned safety and efficacy profile of oral Oxandrolone makes it an appealing adjuvant treatment to counteract the major biologic consequences of a chronically torn rotator cuff (muscle atrophy, fatty infiltration, and intercellular fibrosis), which are known to lead to poor healing and diminished clinical outcomes.^{4,5}

Oxandrolone has been associated with the following side effects:

- Central Nervous System: Habituation, excitation, insomnia, depression, and changes in libido.
- Larynx: Deepening of the voice in females.
- Cardiovascular: Edema
- Breast: Gynecomastia.
- Hepatic: Cholestatic jaundice with, rarely, hepatic necrosis and death. Hepatocellular neoplasms and peliosis hepatis with long-term therapy (see US Boxed Warning below). Reversible changes in liver function tests also occur including increased bromsulphophthalein (BSP) retention, changes in alkaline phosphatase and increases in serum bilirubin, aspartate aminotransferase (AST, SGOT) and alanine aminotransferase (ALT, SGPT).
- Genitourinary: Inhibition of testicular function, testicular atrophy and oligospermia, impotence, chronic priapism, epididymitis, and bladder irritability.
- Hematologic: Bleeding in patients on concomitant oral anticoagulant therapy.
- Metabolic/Endocrine: Decreased glucose tolerance, increased creatinine excretion, increased serum levels of creatinine phosphokinase (CPK). Inhibition of gonadotropin secretion.
- Fluid and Electrolytes: Retention of serum electrolytes (sodium chloride, potassium, phosphate, calcium).
- Musculoskeletal: Premature closure of epiphyses (in children).
- Dermatologic: Acne (especially in females and prepubertal males), hirsutism and male pattern baldness in females.
- Patients with moderate to severe COPD or COPD patients who are unresponsive to bronchodilators should be monitored closely for COPD exacerbation and fluid retention.

Contraindications: nephrosis, carcinoma of breast or prostate, hypercalcemia, pregnancy

US Boxed Warning:

Peliosis hepatitis: A condition in which liver, and sometimes, splenic tissue is replaced with blood-filled cysts which has occurred in patients receiving androgenic anabolic steroids. These cysts may be associated with hepatic dysfunction and even liver failure. This condition is usually completely reversible with cessation of drug.

Protocol Number: APP-17-01020

Version Date: 9/1/2017

Liver cell tumors: Most often benign and androgen-dependent, however, fatal malignant tumors have occurred. Withdrawal of the drug often results in regression or cessation of tumor progression. Hepatic tumors associated with androgens and anabolic steroids are much more vascular than other hepatic tumors and may be silent until life-threatening, intra-abdominal hemorrhage develops.

Blood Lipid Changes: Changes associated with increased risk of atherosclerosis are seen in patients treated with androgens or anabolic steroids, including decreased high-density lipoprotein (HDL) and increased low-density lipoprotein (LDL).

Pregnancy: Oxandrolone is classified as Category X in pregnancy due to teratogenic effects including embryotoxicity, fetotoxicity, infertility, and possible masculinization of the fetus.

Breast Feeding: It is unknown whether Oxandrolone is excreted in human milk. Because of the potential of serious adverse reactions in nursing infants from Oxandrolone, women who are nursing and do not wish to stop may not take part in the study.

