3.0 Study Design

Trial Design

This is a single-center, prospective 1:1 double blind randomized control trial. The trial will be conducted at the University of Southern California (USC), Keck School of Medicine in Los Angeles, California. Patients will be recruited from the Department of Orthopaedics. Men and women, 40–75 years of age, with MRI proven rotator cuff tears, indicated and scheduled for repair will be eligible for inclusion. Men and women with acute tears and those with significant comorbid liver, lung, cardiac, and kidney conditions will be excluded. Women who are pregnant or nursing will also be excluded. Women of child-bearing potential will be required to take a monthly urine pregnancy test and be on an agreed upon contraceptive. Participants will be randomized into one of two groups, a control group (receiving placebo medication) and an experimental group (receiving oral Oxandrolone, 12 mg twice daily for men and 6 mg twice daily for women for 12 weeks). Dosing will begin at the time of surgery and continue for 12 weeks, with medication dispensed by the USC Pharmacy. The study will be double-blinded: neither the treating surgeon nor the patient will know to which group the patient is enrolled.

Surgical Procedure

Arthroscopic inspection of the shoulder will be performed to verify the presence of a rotator cuff tear and to measure the size of the tear. In all cases a standard arthroscopic double-row technique will be used to repair the rotator cuff tendon.^{19,20} Treatment of the biceps tendon, need for subacromial decompression, and/or acromioclavicular joint resection will be at each surgeon's discretion. Intraoperative measurements of rotator cuff tear type and size as well as the details of the surgical procedure will be recorded.

Postoperative Rehabilitation

All participants in the study will undergo a standardized rehabilitation protocol for rotator cuff repair as agreed upon by the surgeons involved. Rehabilitation will be supervised by a licensed physical therapist. Adherence to the rehabilitation protocol will be assessed by review of patient treatment logs. If there are alterations to the standard postoperative rehabilitation course, the treating surgeon will be notified and will determine if the alteration in course warrants removal from the study. Patients who do not meet 80% adherence to the standardized protocol will be considered non-compliant and controlled for in the data analysis.

Feasibility

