The study team has the experience, knowledge, and capability to conduct this study. The surgeons involved perform approximately 400 rotator cuff repairs per year. The study team assembled has conducted similar prospective studies in the past on rotator cuff healing. In addition, the study team has experience with clinical trials involving anabolic steroids.

The collaborative nature of the study is exemplified in the sharing of responsibilities. The majority of the clinical care proposed in this study (demographic data, medical history, physical examinations, vital signs, preoperative MRI without contrast) is standard-of-care treatment for rotator cuff tears all surgeons involved and will be overseen as such. The outcome measures collection will be monitored by a research coordinator through the Department of Orthopaedic Surgery. The research coordinator will be responsible for arranging follow-up care and confirming that postoperative MRI, functional tests, and patient-reported outcome measure are completed. The safety profile including laboratory tests and body composition will be performed under the guidance and monitoring of [name] based on his extensive knowledge of the anabolic steroid field. The body composition measurements will be made in [name]

Protocol Number: APP-17-01020

Version Date: 9/1/2017

laboratory. Postoperative rotator cuff repair rehabilitation and patient-reported outcome data will be overseen by [name], given her career-long expertise in shoulder-specific rehabilitation and shoulder pathology patient-reported outcome measures. In addition, patient recruitment will not be an issue as the study-eligible population significantly overlaps with the patient population most frequently affected by symptomatic, chronic rotator cuff tears.

Key Personnel

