5.0 Selection and Randomization of Subjects

Participants

Men and women, aged 40-75 years, presenting to an orthopaedic surgeon with a full thickness rotator cuff tear will be eligible for study screening. The inclusion and exclusion criteria are listed below.

All eligible patients will receive information about the trial verbally and in writing. After signing written informed consent, they will be randomly allocated to undergo rotator cuff repair followed by standard of care structured rehabilitation with Oxandrolone administration or standard of care structured rehabilitation with placebo. Allocation will be performed using computer software and will occur at the pharmacy to ensure that all investigators are blinded. The USC Pharmacy will prepare sequentially numbered, opaque, sealed envelope containing the assigned interventions to ensure randomness is preserved. The surgeon, PI, study team, and physical therapist will not know to which study arm the patient was randomized. The protocol for rehabilitation will remain the same for all patients. The USC Pharmacy will provide the investigators with a list of all participants and group assigned at the end of the study. Investigators will not have access to the study group assignment for any participant during data collection, to ensure adequate double-blinding of both the investigators and participants.

Inclusion criteria

- Men and women age 40-75 years old who have failed nonoperative management of chronic, full thickness rotator cuff tears confirmed by MRI without contrast

Exclusion criteria

- Patients with prior shoulder surgery or prior rotator cuff repair
- Tears larger than 5cm
- Significant glenohumeral arthritis (Hamada Grade 2 or higher)
- Untreated diabetes mellitus
- Pituitary tumor
- Rheumatoid Arthritis
- Uncontrolled hypertension
- Congestive Heart Failure
- Myocardial Infarction within the past 6 months

- End-stage renal disease
- Liver enzymes two times the normal value
- DVT within the past 6 months
- Disorder of the coagulation system
- Currently taking anticoagulation
- Claustrophobia
- Prior or current use of anabolic steroids
- Chromosomal disorders
- Prostate cancer
- Breast cancer
- Hypercalcemia
- Medications that interfere with testosterone production or function, including but not limited to 5 α -reductase inhibitors

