- Pregnant or breastfeeding, or expecting to conceive **or father** children within the projected duration of the trial, starting with the Screening visit through **6 weeks** after the last dose of study treatment.
- Any other condition or treatment interfering with completion of the trial

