6.0 Study Agent Administration and Safety

Oxandrolone Administration

Oxandrolone will be given to experimental men (12 mg BID) and women (6 mg BID) for 12 weeks starting the day of surgery. Previous clinical studies where oxandrolone was given for greater than 6 months have shown no androgenic effects, behavioral changes, sepsis, hirsutism, or acne in the patient population. Elevated liver transaminase levels have been noted but have been transient and asymptomatic.¹⁻³

Patient Safety and Compliance

Patients will have liver transaminase levels measured when preoperative labs are obtained. Additionally, liver enzymes will be assessed at 2, 6, 12, and 24 weeks after rotator cuff repair. Testosterone levels and a quantitative assay for oxandrolone will also be drawn prior to supplementation, at the 2 week post-operative visit and at the 6 month post-operative visit to assess for compliance. Any adverse medication reaction will be met with cessation of medication, but will continue to be followed for outcome data collection.

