7.0 Clinical and Laboratory Evaluations

Program Time Line

Study participants will be tested on multiple occasions. Information will be collected prior to surgery, followed by measurements on the day of procedure, and 2, 6, 12, 24, 52, and 104 weeks after surgery. Surgery will be performed on an arranged date with the orthopaedic surgeon. Physical therapy will follow a pre-defined protocol with a physical therapist.

Testing Visits

Outcome measures and safety measures will be collected at routine postoperative visits with the operating surgeon. Dates and involved events are described in Table 1 below.

Schedule of Events

Event	Pre-Procedure	Procedure Day	Post-Operative Week					
			2	6	12	24	52	104
Informed Consent	x							
Demographics	x							
Confirm Inclusion/Exclusion Criteria	x	x						
Medical History	x	x						
Vital Signs	x	x	x	x	x	x	x	x
Randomization		x						
Blood draw: Testosterone level and Oxandrolone level	x		x			x		
Blood draw: Liver Enzymes	x		x			x	x	x
Outcomes:								
MRI: rotator cuff healing; Sugaya classification (primary outcome)	x				x		x	x
MRI: Fatty infiltrate (secondary outcome)	x				x		x	x
MRI: Muscle volume (secondary outcome)	x				x		x	x
Body Composition – lean mass & body fat (secondary outcome)	x		x	x	x	x	x	x
Questionnaires: ASES, VAS, PASS (secondary outcome)	x	x	x	x	x	x	x	x
Shoulder Range of Motion (secondary outcome)	x	x	x	x	x	x	x	x
Shoulder Strength (secondary outcome)	x	x	x	x	x	x	x	x

Table 1. Outline of pre- and postoperative timing of events and schedule of data collection.

Demographics.

Demographics of age, height, weight, race, arm dominance, and tear size and location will be recorded.

Inclusion and Exclusion Criteria.

The inclusion and exclusion criteria will be confirmed prior to enrolled, as described above in section 5.0.

Females of reproductive potential (women who have not been post-menopausal for at least 24 consecutive months, ie, who have had menses within the preceding 24 months, or women who have not undergone surgical sterilization, hysterectomy or bilateral salpingectomy or bilateral oophorectomy or tubal ligation) must have a negative serum or urine pregnancy test *with a sensitivity of ≤ 25 mIU/mL* within 48 hours prior to study entry.

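### The section 5.0 exclusion list omits nephrosis, one of five contraindications the protocol states; its only renal entry, end-stage disease, is narrower than the section 3.0 kidney exclusion.

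*Combined protocol and SAP*

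**What the plan says.** Four places in the combined protocol and SAP bear on this point.

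- **Section 4.0, Drug Information**, gives the contraindications to oxandrolone: "Contraindications: nephrosis, carcinoma of breast or prostate, hypercalcemia, pregnancy".
- **Section 3.0, Trial Design**, says that "those with significant comorbid liver, lung, cardiac, and kidney conditions will be excluded". It does not define how serious a kidney condition must be to count.
- **Section 5.0, Participants**, introduces the formal criteria with "The inclusion and exclusion criteria are listed below". The only renal item among the exclusions is "End-stage renal disease". The list closes with a general item: "Any other condition or treatment interfering with completion of the trial".
- **Section 7.0, Inclusion and Exclusion Criteria**, identifies the list used at screening: "The inclusion and exclusion criteria will be confirmed prior to enrolled, as described above in section 5.0".

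Information on a patient's kidneys could come from several sources. Section 3.0 (Feasibility) counts "demographic data, medical history, physical examinations, vital signs, preoperative MRI without contrast" as standard care. Section 7.0 has a medical history questionnaire that covers other illnesses, and its schedule places medical history before surgery and again on the day. Section 6.0 says "Patients will have liver transaminase levels measured when preoperative labs are obtained", but does not say what else those labs contain.

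**The concern.** A condition that the protocol itself calls a contraindication should be a named reason not to enrol. Four of the five were carried from section 4.0 into the section 5.0 list by name and one was not. The documents give no reason for the difference, so it looks like an oversight.

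The renal entry that does appear does not fill the gap, since a patient can have nephrosis without end-stage renal disease. It also sets a narrower bar than the kidney exclusion in section 3.0, so the answer for the same patient can depend on which section the screener has open.

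What is at stake is participant safety and consistent eligibility decisions. The drug is given for 12 weeks as an investigational addition to a planned repair, and section 4.0 lists edema and electrolyte retention among its side effects. The documents do not say why nephrosis is a contraindication, and the point does not depend on the reason.

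**Working it through.** The plan gives no figure to reproduce here, and no sample size, error rate or effect size is involved. The check is a comparison of texts.

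**Step 1. Count the contraindications in section 4.0.** Nephrosis, breast carcinoma, prostate carcinoma, hypercalcemia and pregnancy make 5.

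**Step 2. Look for each one in the section 5.0 exclusions.**

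| Contraindication (section 4.0) | Named in section 5.0? |
|---|---|
| Breast carcinoma | Yes |
| Prostate carcinoma | Yes |
| Hypercalcemia | Yes |
| Pregnancy | Yes, in the pregnancy and breastfeeding item |
| Nephrosis | No |

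Named: 4 of 5. Not named: 5 − 4 = 1.

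**Step 3. Check whether another section 5.0 entry covers nephrosis.** The list has 23 exclusion entries. One is renal (end-stage disease) and none names nephrosis or nephrotic syndrome. The closing general item turns on whether a condition would interfere with completing the trial. A patient with nephrosis might well take the tablets and attend every visit, so that item does not clearly apply. An investigator could stretch it, but it is not worded as a drug-safety criterion.

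**Step 4. Compare the renal wording of sections 3.0 and 5.0.** End-stage renal disease is a subset of significant kidney conditions. For a patient with nephrosis short of end stage:

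- section 3.0 on an ordinary reading: excluded;
- section 5.0 as listed: no named criterion excludes the patient.

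**Step 5. Ask what would bring the diagnosis to light.** The history, taken twice, and the physical examination may reveal it. The blood draws in the section 7.0 schedule are testosterone, oxandrolone and liver enzymes. Because section 6.0 does not list the contents of the preoperative labs, the documents do not show whether renal tests are done, and nothing is assumed either way. A history that reveals nephrosis supplies the fact. The rule for acting on it has to come from the criteria.

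**The case against.** The strongest reply is that the protocol, read as a whole, already keeps these patients out. Section 3.0 is worded as a mandatory exclusion, and nephrosis is a significant kidney condition on any ordinary reading. Sections 3.0 and 5.0 can both be applied, and a narrow entry in one does not permit what a broader entry in the other forbids. The investigator is told of the contraindication in section 4.0, and the history would probably uncover the diagnosis. On this view the gap is one of cross-referencing.

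Much of that stands, and it limits the point in three ways.

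- A reader might infer that section 7.0 makes the section 5.0 list the only gate. It does not. It says the criteria are confirmed as section 5.0 describes them, and it does not set section 3.0 aside.
- A reader might infer that section 4.0 is background with no bearing on who may enter. That is also wrong: the same section bars nursing women who do not wish to stop. Section 7.0 adds pregnancy-test and contraception conditions. Eligibility rules are spread over several sections.
- A reader might infer that patients with nephrosis would be enrolled, or that no renal test is done. The documents support neither inference.

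The reply does not remove the omission. The list named for confirming eligibility, applied as written, contains no criterion that stops a patient in whom the protocol says the drug is contraindicated. If a statement in section 4.0 were enough, the other four contraindications would not have needed repeating. That eligibility is scattered over several sections is a reason to make the screening list complete.

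**Conclusion.** The point holds as a gap in alignment: one of five stated contraindications is missing from the section 5.0 list, and the only renal entry there is narrower than the section 3.0 exclusion. It should be corrected because it concerns participant safety and costs almost nothing.

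The likely consequence is small. No prevalence is given or assumed, so the number of affected patients cannot be calculated. The expectation that it is zero rests on two assumptions: that screeners also apply section 3.0, and that the history reveals the diagnosis. If a screener worked only from the section 5.0 list, such a patient would meet no named exclusion.

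**What to change.** Keep the end-stage renal disease entry and add one bullet to the section 5.0 exclusion list: *Nephrosis (nephrotic syndrome)*. All five contraindications would then be named, and sections 3.0 and 5.0 would agree for this patient.

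The cost is a minor amendment and the possible loss of a very rare candidate. No visit, laboratory test or numerical threshold is added.

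A broader rewording, replacing the end-stage entry with significant kidney disease, is not recommended. It would match section 3.0 in full, but it would swap a clear entry for an undefined one, and the documents do not allow its effect on recruitment to be judged. The single bullet leaves sections 3.0 and 5.0 different in breadth for other kidney disease. Closing that difference would require the sponsor to define what counts as significant, which is a separate decision.

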Females of reproductive potential must agree not to participate in the conception process (ie, active attempt to become pregnant, in vitro fertilization), and if participating in sexual activity that could lead to pregnancy, must use at least one reliable form of contraceptive. Female subjects must use contraceptives *while receiving study treatment and for 6 weeks* after stopping study treatment.

Protocol Number: APP-17-01020

Version Date: 9/1/2017

Acceptable forms of contraceptives include:

- *Condoms (male or female) with or without a spermicidal agent*
- *Diaphragm or cervical cap with spermicide*
- *Intrauterine device (IUD)*
- *Hormonal contraceptive*

NOTE: Written self-reported or partner reported sterility or lack of reproductive potential will be acceptable in place of contraceptive use.

Medical History.

A standard medical history questionnaire will be completed by the participant of past medical history of their shoulder pain, co-morbidities, and medical history of all other conditions.

Vital Signs.

Vital signs of temperature, blood pressure, respiration rate, and heart rate will be recorded.

Blood Draws

As described above, blood will be collected to monitor any adverse effects on the participant's health and to assess for medication compliance.

Outcomes:

MRI rotator cuff healing; Sugaya classification (Primary outcome). All participants will have a standardized MRI T2-weighted images without contrast, and used to classify rotator cuff integrity using 5 categories of the Sugaya classification. The 5 categories are: type I= rotator cuff sufficient thickness with homogeneously low intensity on each image; type II= rotator cuff sufficient thickness, partial high-intensity area; type III= insufficient rotator cuff thickness with less than half the thickness as compared to normal cuff, but without discontinuity; type IV= minor rotator cuff discontinuity with only 1 – 2 slices on imaging that suggest a small full-thickness tear; and type V= major discontinuity observed in more than 2 slices on imaging, suggesting a medium or large full-thickness tear.³³

MRI: Fatty infiltrate (Secondary outcome). All participants will have a standardized MRI T2-weighted images without contrast. The Goutallier grading classification⁷ will be used to assess fatty infiltration on 5 categories of grade 0= no fatty infiltration; grade 1= some fatty streaks; grade 2= less fat than muscle; grade 3= as much fat as muscle; and grade 4= more fat than muscle.

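### Nephrosis is a stated contraindication to oxandrolone in section 4.0 but is not an exclusion in section 5.0; the lung exclusion in section 3.0 is not carried into that list either

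*Combined protocol and SAP*

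**What the plan says.** Section 4.0 (Drug Information) states: "Contraindications: nephrosis, carcinoma of breast or prostate, hypercalcemia, pregnancy".

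Section 5.0 (Exclusion criteria) lists prostate cancer, breast cancer, hypercalcemia and pregnancy. Nephrosis does not appear. The one kidney item is "End-stage renal disease", and the list closes with a catch-all: "Any other condition or treatment interfering with completion of the trial". No item concerns the lung.

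Section 3.0 (Trial Design) gives a broader summary: "those with significant comorbid liver, lung, cardiac, and kidney conditions will be excluded". It defines neither the conditions nor a threshold for them.

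Section 7.0 says which list is used at screening: "The inclusion and exclusion criteria will be confirmed prior to enrolled, as described above in section 5.0".

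**The concern.** A condition the protocol names as a contraindication should be an explicit exclusion. Four of the five were carried over by name and no reason is given for the fifth, so this looks like an oversight.

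A screener working from section 5.0 has no line telling them to exclude a patient with nephrosis short of end-stage renal disease. Such a patient could be randomized to 12 weeks of oxandrolone. Section 4.0 lists edema and electrolyte retention among the drug's effects. The dose in men is 24 mg/day, which section 1.0 acknowledges is above the approved adult maximum of 20 mg/day.

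The lung point is of a different kind. Section 3.0 promises an exclusion that the operative list does not contain, so the two sections disagree about who is eligible.

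**Working it through.** The plan gives no figure to reproduce here. The check is an item-by-item comparison of the lists.

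**Contraindications (section 4.0) against exclusions (section 5.0)**

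| Section 4.0 | Named in section 5.0? |
|---|---|
| Nephrosis | No |
| Breast carcinoma | Yes |
| Prostate carcinoma | Yes |
| Hypercalcemia | Yes |
| Pregnancy | Yes |

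Four of five are named, and 5 − 4 = 1 is missing.

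**Organ systems (section 3.0) against exclusions (section 5.0)**

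| Section 3.0 | Item in section 5.0 |
|---|---|
| Liver | Enzymes at twice normal |
| Cardiac | Heart failure, recent infarction, uncontrolled hypertension |
| Kidney | End-stage renal disease |
| Lung | None |

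Three of four systems have at least one item; lung has none.

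**Does other text in section 5.0 cover nephrosis?** The kidney item describes the late stage of renal failure and does not capture all nephrosis. The catch-all is worded around finishing the trial. A patient with nephrosis could attend every visit, so the wording does not clearly reach drug risk.

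**Would the screening procedures find it?** Table 1 schedules medical history at 2 points, before the procedure and on the procedure day. Section 7.0 describes it this way: "A standard medical history questionnaire will be completed by the participant", covering co-morbidities and other conditions. A known diagnosis would probably come to light, but section 5.0 would still not say to exclude it.

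For an undiagnosed case, Table 1 has 2 blood-draw rows. One is "Blood draw: Testosterone level and Oxandrolone level" and the other is liver enzymes, so 0 of 2 is a kidney test. Section 6.0 says: "Patients will have liver transaminase levels measured when preoperative labs are obtained". It does not itemize the rest of that preoperative set.

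**Chance of exposure.** Allocation is 1:1 (section 3.0), so an enrolled patient with nephrosis has probability 1/2 = 50% of receiving oxandrolone. This follows from the allocation ratio alone and says nothing about how many such patients there would be.

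**The case against.** The strongest reply is that the protocol should be read as a whole. Section 3.0 is current text and excludes significant kidney conditions, and a kidney disorder listed as a contraindication is naturally read as significant. Section 7.0 points to section 5.0 without withdrawing section 3.0. The catch-all could also be read to cover nephrosis, since completing the trial includes completing 12 weeks of drug. On this view only a checklist is incomplete.

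This is a fair argument for low severity, but it does not remove the gap. The section 3.0 sentence is an undefined summary, whereas section 5.0 is the list confirmed at screening and names only end-stage disease for the kidney. A careful screener might infer the exclusion, but the protocol does not instruct it.

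Three further points stand:

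- The unlisted preoperative labs may include renal tests as standard care, so the count of study blood draws does not show that kidney disease goes untested. It shows only that the protocol specifies no such test.
- Adding nephrosis to the list would not detect an undiagnosed case. Hypercalcemia is in the same position: it is a named exclusion with no calcium test in Table 1.
- Lung disease is not a contraindication in section 4.0, which asks only for monitoring in some patients with COPD. The mismatch could instead be resolved by trimming section 3.0.

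**Conclusion.** The concern holds, as a minor point of patient safety and eligibility consistency. One of five stated contraindications is missing from the operative exclusion list, and nothing in that list clearly stands in for it. The lung mismatch between sections 3.0 and 5.0 is real but secondary. Whether end-stage renal disease is what section 3.0 means by a significant kidney condition is unclear; that is a question for the team, not a demonstrated error.

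The conclusion rests on two readings: that section 5.0 governs screening, as section 7.0 says, and that nephrosis can exist without end-stage renal disease. The documents give no frequency of nephrosis or lung disease in this population, so the practical effect cannot be sized. The sample size of 116 and the primary analysis do not depend on this point.

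**What to change.** 1. Add nephrosis to the section 5.0 exclusion criteria. This is the essential change.
2. Add a lung criterion to section 5.0 that carries over the section 3.0 exclusion, with the clinical team setting the threshold. The COPD wording in section 4.0 is one possible basis, though there it is a monitoring precaution only.
3. Ask the team to confirm whether end-stage renal disease is the intended kidney threshold, and align sections 3.0 and 5.0 with the answer.

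The cost is two lines of text and one clinical decision. The downside is possibly a few fewer eligible patients. Section 3.0 reports about 400 repairs a year by the participating surgeons, against a target of 116.

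### Lipid change and reduced glucose tolerance are listed as oxandrolone effects, but no visit names a lipid or glucose test

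*Combined protocol and SAP*

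**What the plan says.** Section 4.0 (Drug Information) describes the lipid effect under the US Boxed Warning heading: "Blood Lipid Changes: Changes associated with increased risk of atherosclerosis are seen in patients treated with androgens or anabolic steroids". It specifies that HDL falls and LDL rises. Its side-effect list includes "Metabolic/Endocrine: Decreased glucose tolerance" and, under fluids and electrolytes, "Retention of serum electrolytes (sodium chloride, potassium, phosphate, calcium").

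Section 6.0 sets out the blood tests. For the liver: "Patients will have liver transaminase levels measured when preoperative labs are obtained", and "Additionally, liver enzymes will be assessed at 2, 6, 12, and 24 weeks after rotator cuff repair". For compliance: "Testosterone levels and a quantitative assay for oxandrolone will also be drawn prior to supplementation", then at week 2 and month 6. Its safety rule is "Any adverse medication reaction will be met with cessation of medication", with follow-up continuing.

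Table 1 in Section 7.0 has two blood-draw rows, one for testosterone and oxandrolone and one for liver enzymes. The Blood Draws paragraph in the same section says that blood serves to watch for adverse effects and to check compliance, but it refers back to tests already described and adds none. Section 3.0 (Feasibility) mentions safety laboratory tests without naming any.

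**The concern.** The plan names a hazard and then schedules nothing that would detect it. Neither a lipid shift nor a modest rise in glucose need cause symptoms. Vital signs and body composition do not measure them, and the stopping rule cannot act on a laboratory change that nobody measures.

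Two features make this more than a routine wish for extra laboratory tests. The first is the dose. Section 1.0 says the proposed dose is unstudied, puts men above the approved maximum, and says adverse events generally depend on dose. The second is who can enter. Patients are aged 40 to 75, and only untreated diabetes is excluded, so patients with treated diabetes are eligible.

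What is at stake is the safety of participants during dosing and the balance of benefit and risk at the end. If oxandrolone improved tendon healing, the trial could not say at what metabolic cost. On-treatment values cannot be recovered later unless samples are kept.

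**Working it through.** The plan states no figure to reproduce. The check compares the effects listed in Section 4.0 with the entry criteria (Sections 3.0 and 5.0) and with every test named in Sections 3.0, 5.0, 6.0 and 7.0.

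| Effect in Section 4.0 | Relevant entry criteria | Test named during dosing |
|---|---|---|
| Liver injury (boxed-warning heading) | Significant liver disease; raised liver enzymes | Liver enzymes |
| Harm in pregnancy (same heading) | Pregnancy excluded; contraception required | Monthly urine pregnancy test |
| Lower HDL, higher LDL (same heading) | No lipid criterion; cardiac and blood-pressure exclusions | None |
| Reduced glucose tolerance | Untreated diabetes only | None |
| Calcium retention | Hypercalcemia excluded | None |

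Among these hazards under the boxed-warning heading, the lipid effect is the one with no related test.

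**Blood draws during dosing.** Section 6.0 gives three (weeks 2, 6 and 12). Table 1, as extracted, marks one (week 2): its liver row has pre-procedure and weeks 2, 24, 52 and 104. Both sources give five liver timepoints, so a shift of columns in the table is possible. Against that, the testosterone and oxandrolone row directly above agrees with Section 6.0. On either reading, the number of lipid or glucose tests is zero.

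**Dose** (Sections 1.0 and 6.0).
- Men: 2 × 12 = 24 mg/day, and 24/20 = 1.20 of the approved maximum. Over 12 × 7 = 84 days this is 24 × 84 = 2016 mg, against 20 × 84 = 1680 mg at the maximum, a difference of 336 mg.
- Women: 2 × 6 = 12 mg/day, and 12/20 = 0.60 of the maximum.

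**Patients exposed** (Section 10.0). There are 58 per arm, or 52 after planned attrition. The sex split is not given. If 40% to 60% are men (an assumption), 0.40 × 58 ≈ 23 to 0.60 × 58 ≈ 35 drug-arm patients exceed the approved maximum.

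**Samples for the fix.**
- Pre-procedure and weeks 2, 6, 12 and 24: 116 × 5 = 580.
- Of these, during dosing: 116 × 3 = 348, with 58 × 3 = 174 in the drug arm.
- Extra draws if weeks 6 and 12 are not really planned: 116 × 2 = 232.

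**The case against.** The strongest reply is that the exposure is short and the risk already reduced. The Section 1.0 sentence that ties adverse events to dose ties them to duration as well, and dosing stops at 12 weeks. The stated lipid hazard is a raised risk of atherosclerosis, and nothing in the documents shows what 12 weeks would do to it. Significant cardiac disease, uncontrolled hypertension, heart failure and recent myocardial infarction are all excluded. Women stay well below the approved maximum. All of this stands and keeps the point modest. It does not supply an on-treatment measurement. The short-term reassurance at up to 80 mg/day in Section 1.0 concerns serious liver toxicity only.

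A second reply is that unnamed tests may be meant, since Section 6.0 refers to preoperative labs and Section 3.0 to laboratory tests. The preoperative labs could give baseline values at most, and the Section 3.0 reference names no analyte.

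A third is that the choice of analytes is arbitrary, because sodium, potassium, phosphate and creatine phosphokinase are listed in Section 4.0 and also go untested. This is right for calcium. Hypercalcemia is already an entry exclusion, and sharing a sample is no reason to prefer calcium to the other electrolytes. Lipids are distinguished by their place under the boxed-warning heading, and glucose by the eligibility of treated diabetes. Fasting glucose would still capture glucose tolerance only in part.

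**Conclusion.** The point holds as a modest safety improvement. No lipid or glucose test is named at any visit, so about 58 drug-arm patients would complete 12 weeks of dosing without one. An assumed 23 to 35 of them would be men taking 20% more than the approved maximum.

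Three stronger readings are tempting but unsupported:
- A reader might infer that patients will be harmed or that the dose is unsafe. The documents give no expected size of lipid or glucose change, so no harm can be quantified. The above-maximum argument applies to men only.
- A reader might infer that the trial result is compromised. The Sugaya endpoint and its analysis do not depend on these tests.
- A reader might take three draws during dosing as settled and conclude that the fix needs no new needle-stick. Table 1 marks only one.

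The conclusion assumes that the personnel pages of Section 3.0, which were not in the text reviewed, hold no laboratory schedule.

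**What to change.** 1. Add HDL, LDL and glucose (fasting where feasible) to the samples at pre-procedure, week 2 and week 24, and to the Section 6.0 liver draws at weeks 6 and 12. Week 24 would show whether values recover after dosing ends.
2. Add these rows to Table 1 and correct it to show the week 6 and week 12 draws.
3. Add to Section 10.0 a descriptive report of change from baseline by arm.
4. Do not give routine lipid values to staff who assess outcomes, because a fall in HDL could hint at allocation. The fix needs no larger scheme for holding results.
5. Calcium is optional.

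The cost is an amendment to Sections 6.0, 7.0 and 10.0, routine assays on up to 580 samples, fasting at some visits, and a small residual unblinding risk. No visit is added. If Section 6.0 is the true schedule, no draw is added either. If Table 1 is, the cost is up to 2 extra draws per patient, 232 in all.
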